Kinematics in Posterior Cruciate Retaining and Bi-Cruciate Retaining Total Knee Replacements

[name].
Tennessee Orthopaedic Clinics
[name]
Knoxville, TN 37923

[name].
Erlanger Orthopaedics
[name]
Chattanooga, TN 37403

In vivo knee kinematics will be assessed for 80 subjects that have been implanted with either a Smith & Nephew Journey II posterior cruciate retaining (PCR) [40 subjects] or bi-cruciate retaining (BCR) [40 subjects] total knee arthroplasty (TKA) who are patients of [name] or [name]. Enrollment and testing will be increased to 45 patients per implant model to ensure the necessary 80 usable datasets are acquired and also to account for any subjects that may drop out of the study. All TKAs should be judged clinically successful (KSS > 80). A KSS score of greater than 90 is deemed to be excellent by the Knee Society. Each subject should have a well-functioning prosthesis, be at least three months post-operative, and should have good-to-excellent post-operative passive flexion.

Deciding which patients received which kind of implant was up to the discretion of [name] or [name], according to their professional opinions. The determination as to which type of implant patients received is outside the scope of this particular study. Subjects will already have the knee implants and must be at least three months post-operative. Bilateral subjects will not be included in the study populations.

Inclusion criteria:

1. Subjects will have either a Smith & Nephew Journey II posterior cruciate retaining (PCR) [45 subjects] or bi-cruciate retaining (BCR) [45 subjects] TKA.
2. Patients must be at least three months post-operative.
3. Participants must be judged clinically successful with their most recent new Knee Society score equal to or greater than 80.
4. Weigh < 250
5. BMI < 40
6. Must be >40 years of age
7. Participants must be able to perform the required activities without concern.
8. Subjects must be willing to sign the Informed Consent (IC) form to participate in the study.

Exclusion criteria:

1. Pregnant, potentially pregnant, lactating females or of childbearing age. To satisfy radiation protocol, each female subject will be asked if she is pregnant, or possibly could be pregnant. A pregnant person will not be allowed to participate in the study.
2. Subjects without the required type of knee implant.

3. Cannot not have pain in other parts of the body that would prohibit the patient from performing the activities
4. Cannot have ligamentous pain and/or laxity.
5. Unwilling to sign IC form.
6. Does not speak English.

Study locations

Subject Recruitment:

Research Foundation of [name]

[name]

Knoxville, TN 37923

[contact]

Erlanger Orthopaedics

[name]

Chattanooga, TN 37403

[contact]

Fluoroscopic exams:

Tennessee Orthopaedic Clinic

[name]

Knoxville, TN 37923

[contact]

Study data analysis:

Science and Engineering Research Facility

[name]

Knoxville, TN 37996

CMR Administrative offices:

[name]

[name]

Knoxville, TN 37996

[contact]

Recruitment

Up to forty-five patients will have been implanted with a Smith & Nephew Journey II posterior cruciate retaining (PCR) and 45 patients will have been implanted with a bi-cruciate retaining (BCR) whose post-operative conditions permit them to capably perform the study activities. Research staff from [name] Foundation or [name] practice at Erlanger Orthopaedics will determine potential participants for the study by reviewing medical files. The surgeon's research staff will review the patient's KSS, clinical dictation, and electronic health record (EHR), and he will approve or reject the patient as a candidate for the study. During review of medical files, the research staff will utilize the CMR Recruitment/Enrollment checklist (Attachment 6) to ensure that each potential subject meets all eligibility requirements prior to being contacted. This sheet included a checklist of the inclusion criteria, as well as a field for the

research staff to include a subject identifier so the subject's eligibility can once again be confirmed on the day of data collection. Once this sheet has been completed by the staff, it will be submitted to a UT Research Coordinator, lead researcher or PI/Co-PI/Sub-I to review and authorize recruitment and enrollment. After a potentially eligible subject has been identified and authorized to be enrolled in the study, s/he will be contacted for a visit to the surgeon's office to be consented. The subject will then be consented and scheduled for fluoroscopy data collection at the Tennessee Orthopaedic Clinic in Knoxville, TN. All testing collection at Tennessee Orthopaedic Clinic will be scheduled after normal clinic hours so as not to interfere with the patient treatments occurring during the day.

Data Collection

University of Tennessee researchers with experience conducting fluoroscopic research studies, as well as either a PI/Co-PI/Sub-I for the study, and possibly [name] staff will be present during the fluoroscopy procedure to walk subjects through the activities. A radiation technician (RT) employed by the Tennessee Orthopaedic Clinic will collect fluoroscopic video while subjects perform the following activities: walking up and down a ramp, deep knee bend and rising from the DKB position.

Prior to starting data collection, UT researchers will complete the second portion of the CMR Recruitment/Enrollment checklist to ensure subjects meet eligibility requirements to document inclusion criteria for compliance purposes. Age and weight will be verified at the time of fluoroscopy to ensure eligibility. If a subject does not meet the inclusion criteria, s/he will not be tested. If the participant still meets all study criteria, s/he will be asked to practice the activities to ensure s/he can comfortably complete them and experience no pain with the clinic fluoroscopy machine off (no radiation). The practice portion of the data collection without radiation will not be video-recorded. During the fluoroscopy procedure, the RT will follow the motion of the implanted knee with the fluoroscopy machine; only the knee joint (from the fluoroscopy machine) will be recorded on the fluoroscopy footage. The participant will be allowed to rest as necessary and be instructed to stop the activity at the first sign of pain.

Multiple trials of each activity may be conducted to ensure usable images have been acquired to complete the study. Radiation time will be kept as low as reasonably achievable (ALARA) and will not exceed two minutes. The RT will start the fluoroscope just prior to the subject beginning each activity trial and will stop the fluoroscope immediately after the subject completes each activity trial to ensure that the subject is not exposed during idle periods.

The fluoroscopic footage for these activities will be stored on digital video files on a secure computer workstation, uploaded onto the secure CMR database by the UT researcher that attended data collection, where identifiable data will be removed and substituted for data that cannot identify the subject (e.g., dates of birth will be removed and replaced with number of months the individual has been alive). Subjects will be assigned study and subject-specific identifiers which is how the system will distinguish the datasets.

SPECIFIC RISKS AND PROTECTION MEASURES

1. Fluoroscopic Procedures

Page 3 of 29

As with every clinical study, there may be some risks. However, doses of radiation exposure received will be much lower than those known to produce detectable health effects. Previously reported literature shows that fluoroscopy-based procedure (angiography) on the lower limb result in a typical effective dose of 0.83 mSv per min (0.0083 rem per min) (Verdun¹). Mettler, et al have reported that the typical effective dose for a conventional knee procedure is 0.005 mSv (0.00005 rem)². According to either estimate, the additional risk of a fluoroscopic procedure involving the knee ranges between "Negligible" to "Low" for a 2 minute exam (Verdun). A previous fluoroscopy TKA study conducted at another hospital with a 2 minute on-time limit shows that the average effective dose was 0.14 mSv (0.0014 rem) with a maximum dose of 0.27 mSv (0.0027 rem). The additional risk for all subjects in this previous study would be considered "Negligible". To account for subject variability and differences in imaging techniques, all subjects enrolled in this study will receive less than 4 rem. 4 rem is considered "Very Low" risk. It is unlikely that anyone in this study will approach the 4 rem limit. Since the fluoroscopy data will be collected in one session, there will only be one day in which the participants will be exposed to this amount of radiation.

In conclusion, a participant who will be fluoroscoped for less than two minutes will be exposed to a *maximum* amount of only 4.0 rems of radiation. This means that the maximum total exposure rate will be less than 4 rems per subject for the entire experiment (Attachments 3 and 4). The participant's knee joint will be fluoroscoped using minimal risk levels of radiation according to published literature (Attachment 2).

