## DATA ANALYSIS

Once the subjects have completed the activity, the fluoroscopic videos will be stored digitally and specific frames of interest will be captured from the video and exported into the preprocessing software. The specific frames of interest will be full extension, maximum knee flexion (both inclusive), and 30° knee flexion increments during the complete flexion cycle.

Our 3D to 2D registration technique will be used to overlay the 3D models of the implanted components on their projection in the 2D fluoroscopic image. The fluoroscopic video would be digitized into frames and corrected for distortion. From here, the distortion-free images would be used with the 3D to 2D registration technique to extract *in vivo* patient femorotibial kinematics, which involves overlaying the 3D models of the components on their projection in the 2D fluoroscopic image.

Statistical analysis of the data will be carried out to analyze the two cohorts. All variables, except for lift-off and VAG, will be denoted as continuous. The data will be first checked for normality using the Shapiro-Wilk test. Only when the data is found to be normally distributed will parametric tests be used; otherwise, non-parametric tests will be used. The data will also be tested for equality of variance using the Barlett's test and Levene's test. The final selection criterion for the type of test to conduct will be based on the check for normality, as well as the check for equal variance. Therefore, for all the continuous variables, the following tests will be used:

1. Student's t-test (when the data is normally distributed and has equal variance).
2. Welch Anova test (when the data is normally distributed but has unequal variance).
3. Wilcoxon Mann Whitney U-test (when the data is not normally distributed).

Lift-off, as applicable, will be treated as a categorical variable in this study and a contingency analysis using the Fisher's exact test will be carried out. All statistical tests will be carried out at 95% confidence level ( $\alpha=0.05$ ) and will be performed using JMP® Statistical DiscoveryTM (SAS Institute Inc., Cary, NC) software.

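### Implants were chosen at the surgeons' discretion and follow-up time has no upper limit, but the SAP compares the two cohorts only with unadjusted tests, so any imbalance in surgeon or follow-up that affects kinematics stays in the implant contrast

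*Protocol*

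**What the plan says.** **How the cohorts arise.** The protocol's opening description states: "Deciding which patients received which kind of implant was up to the discretion of" the two surgeons. It adds: "The determination as to which type of implant patients received is outside the scope of this particular study". Patients already have their implants when recruited.

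**Where patients come from.** One surgeon practises in Knoxville and the other in Chattanooga. Under Recruitment, candidates are found by the Knoxville foundation's research staff or by staff of a surgeon's "practice at Erlanger Orthopaedics will determine potential participants for the study by reviewing medical files".

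**Time since surgery.** Inclusion criterion 2 reads: "Patients must be at least three months post-operative". No upper limit is given.

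**Screens common to both cohorts.** These are a Knee Society Score (KSS) of at least 80, limits on weight, BMI and age, no ligamentous pain or laxity, no bilateral subjects, a well-functioning prosthesis and ability to do the activities. Subjects also "should have good-to-excellent post-operative passive flexion".

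**Where outcomes are measured.** Study locations and Data Collection place all fluoroscopy at one Knoxville clinic, filmed by a technician whom that clinic employs. One facility analyses the data.

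**Analysis.** The SAP's DATA ANALYSIS section says: "Statistical analysis of the data will be carried out to analyze the two cohorts". Continuous variables go to Student's t-test, Welch ANOVA or Mann-Whitney, and lift-off to Fisher's exact test, all at alpha 0.05. The choice of test rests on distributional checks: "Only when the data is found to be normally distributed will parametric tests be used". The text available contains no covariate, stratification, matching or table comparing the cohorts.

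**The concern.** A two-sample test estimates the difference between the cohorts as they stand. When the surgeon chose the implant, that difference carries the implant effect together with anything else that differs between the cohorts and affects kinematics. Two such factors can be identified from the documents: who operated, and how long after surgery the knee was filmed. The SAP's normality and variance checks do not address either, and the planned tests would not show whether an imbalance exists.

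What is at stake is interpretation. The protocol's Benefits section lists better future implant designs, drawn from the kinematic findings, among the potential benefits. A reader using the results that way would credit the implant with a difference that could belong partly to surgeon or to follow-up time.

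**Working it through.** **The plan's own figures.** The protocol targets 40 usable datasets per implant and enrols 45. The implied loss is 1 − 40/45 = 11.1%. No effect size, SD or power is given, so there is no power calculation to reproduce. The documents also give no surgeon-by-implant split, no follow-up distribution and no surgeon effect. Every input below except n = 40 per group and alpha = 0.05 is therefore an assumption. The test is taken as two-sided, which the SAP does not state.

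**1. Surgeon imbalance, unadjusted t-test, no implant effect.** Let g be the surgeon effect in units of the within-surgeon SD. Let one surgeon supply a share p of one cohort and 1 − p of the other.

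- Bias = g × (2p − 1).
- Approximate SE = √(1 + g²p(1 − p)) × √(2/40).
- At p = 0.8, g = 0.3: bias = 0.3 × 0.6 = 0.18; SE = 1.007 × 0.2236 = 0.225; ratio = 0.80; rejection about 12.6%.
- At p = 0.8, g = 0.5: bias = 0.5 × 0.6 = 0.30; SE = 1.020 × 0.2236 = 0.228; ratio = 1.32; rejection about 26.0%.

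Simulating the t-test itself (100,000 runs per cell, surgeon shares fixed) gives slightly lower rates:

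| Surgeon split by implant | g = 0.3 SD | g = 0.5 SD |
|---|---|---|
| 50/50 | about 5% | about 4% |
| 60/40 | 5.5% | 6.5% |
| 70/30 | 8% | 13% |
| 80/20 | 12% | 25% |
| Surgeon and implant coincide | 26% | 60% |

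With balanced surgeons there is no inflation.

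**2. Follow-up imbalance.** Bias = (within-cohort correlation of months with outcome) × (gap in mean months, in SD). Rejection comes from the noncentral t with 78 df and noncentrality bias/√(2/40).

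- Correlation 0.2, gap 0.5 SD: bias 0.10, noncentrality 0.447, rejection 7.3%.
- Correlation 0.3, gap 1 SD: bias 0.30, noncentrality 1.342, rejection 26.3%.

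**3. Precision cost of a surgeon term.** SE factor = 1/√(1 − (2p − 1)²). The difference detectable with 80% power is 0.634 SD times that factor.

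| Split | SE factor | Detectable difference |
|---|---|---|
| 50/50 | 1.00 | 0.63 SD |
| 60/40 | 1.02 | 0.65 SD |
| 70/30 | 1.09 | 0.69 SD |
| 80/20 | 1.25 | 0.79 SD |
| 90/10 | 1.67 | 1.06 SD |

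The other covariates may add to this.

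**4. What adjustment cannot do.** Suppose surgeons are balanced but an unrecorded patient factor worth 0.5 SD is split 80/20 by implant. The bias is again 0.5 × 0.6 = 0.30, and a surgeon-adjusted model still rejects about 25% of the time.

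**The case against.** **The comparison is descriptive.** The SAP claims no causal effect, and the protocol openly sets implant choice aside. If the aim is only to describe two cohorts, a real difference in their means is not an error. That stands as a limit: the documents do not support saying that the plan makes a causal claim. But hypothesis tests at alpha 0.05, with implant design named as a potential use, make an implant reading likely enough to guard against.

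**The screens already deal with surgeon and recovery.** This stands in part. The KSS form scores alignment, instability, range of motion, contracture and extensor lag. Together with the laxity exclusion and a pain-free practice run, it removes poor results whatever the surgeon or follow-up time. A reader might infer that nothing in the plan acts on these pathways, and that would be wrong. The screens narrow both cohorts, but they do not balance them.

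**Two practices might suggest two measurement sites.** The documents exclude this. Outcomes are filmed at one clinic and analysed at one facility by one registration method.

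**All magnitudes are assumed.** This stands. Whether a surgeon effect of 0.3 to 0.5 SD survives the screening is unknown.

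**Adjustment does not reach the reason for the choice.** This also stands, as step 4 shows. Tables and cautious wording help in every case; the model helps only with the factors it contains.

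**Conclusion.** The concern holds as a limited one that should be fixed. The comparison is non-randomised, follow-up time is open-ended, and the SAP text available has no means of detecting or removing an imbalance in surgeon or follow-up. The size and direction of any bias cannot be derived from the documents, and it may be nil. The 12 to 25% range rests wholly on an assumed 80/20 split and a 0.3 to 0.5 SD surgeon effect; balanced surgeons would give no inflation.

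Two stronger readings should be resisted. A reader might infer that surgeon and implant coincide, partly because the Attachment 6 checklist names only the BCR implant beside an item on whose patient it is. The surgeon's name in that item is removed, so it shows nothing about the split. A reader might also infer that an adjusted analysis would isolate the implant effect. It would not, because the documents show no field recording why each implant was chosen.

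**What to change.** 1. Tabulate implant by surgeon, and months since surgery and age by implant.
2. In every case, report results as associations. State that the reason for implant choice is not recorded and may still confound an adjusted result.
3. If both surgeons contribute to both cohorts, make the main comparison of each continuous variable a linear model with implant, surgeon, months since surgery and age. Surgeon and practice are one term. Give the adjusted difference with a 95% CI, check the residuals, and use robust standard errors if the checks fail. For lift-off, use an exact test stratified by surgeon, and say that it adjusts for surgeon only. Keep the planned tests as sensitivity analyses.
4. If either surgeon contributes no patients to one cohort, report an implant-plus-surgeon difference, because no model separates the two. If overlap is small, report the adjusted estimate with its wide interval.

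**Cost.** SAP wording, two tables and a data-transfer check. Surgeon and surgery date are fields on Attachment 6. The KSS form in Attachment 5 also asks for both and is not specific to an implant, so it covers PCR patients. Age in months is kept at de-identification (Data Collection). If the named software lacks a stratified exact test, the SAP should name one that has it. The loss of precision from the surgeon term is small unless the split is strong: an SE factor of 1.09 at 70/30, but 1.67 at 90/10.

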<0.1	<10 ⁻⁶	Negligible	Radiography of the chest (postero-anterior), extremities, or teeth
0.1–1.0	10 ⁻⁵	Minimal or extremely low	Abdomen, lumbar spine
1.0–10	10 ⁻⁴	Very low	CT of the brain, chest, or abdomen
10–100	10 ⁻³	Low	Multiphase CT
>100	>10 ⁻²	Moderate	Interventional procedures,* repeat CT

Sources.—References 10 and 22.

*Including the determinist effects of ionizing radiation (skin burns).

ATTACHMENT 2

Mettler, et al. "Effective Doses in Radiology and Diagnostic Nuclear Medicine." *Radiology* 248.1 (2008): 254-263. <http://radiology.rsna.org/content/248/1/254.full.pdf+html>

Results

Representative values and ranges of effective doses reported in the literature for various examinations and procedures are presented in Tables 1-5.

In addition to effective dose, absorbed organ doses are important for some procedures that either involve high doses or include sensitive tissues in the primary radiation beam. For CT scanning, organs in the beam can receive doses that are 10-100 mGy but are usually in the range of 15-30 mGy per single CT sequence (162-169).

Doses to the lens of the eye during CT scanning of the head have been reported to be 30-50 mGy (170-174). Values depend on whether the lens is in the direct beam or out of the beam when the gantry is angled. Angulation of the gantry for head CT studies can reduce the eye dose by 90%, to about 3-4 mGy. For many new scanners, such as portable intensive care unit scanners, positron emission tomography/CT scanners, and dual-tube multidetector CT scanners, the gantry cannot be angled, which will result in higher eye doses when head CT examinations are performed.

Radiation dose to the breast tissue is of critical importance, especially in girls and young women. Chest CT scanning results in relatively high doses to breast tissue. Doses have been estimated to be 20-60 mGy for a CT examination performed for pulmonary embolism, 50-80 mGy for a CT coronary angiography examination, and even 10-20 mGy to the inferior part of the breast for an abdominal CT examination (175-177). Even though lower x-ray energies are used, as a comparison, for mammography, the American College of Radiology and the Mammography Quality Standards Act of 1992 regulations require that the mean glandular dose for a single mammogram to a normal-sized breast with 50% glandularity be less than 3 mGy.

Discussion

As mentioned earlier, effective dose is a calculated age- and sex-averaged value

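### The 4 rem dose cap is 40 mSv, which the protocol's own table rates Low (10⁻³), not Very Low (10⁻⁴); separately, four rem conversions are ten times too small

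*Protocol*

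**What the plan says.** All of this is in the Protocol, Specific Risks and Protection Measures, item 1 (Fluoroscopic Procedures), and the attachments it relies on.

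- **The cap.** "all subjects enrolled in this study will receive less than 4 rem", and in the section's conclusion "the maximum total exposure rate will be less than 4 rems per subject for the entire experiment".
- **The label on the cap.** "4 rem is considered 'Very Low' risk".
- **The doses used for comparison.** For lower-limb angiography, "a typical effective dose of 0.83 mSv per min (0.0083 rem per min"); for a plain knee examination, "typical effective dose for a conventional knee procedure is 0.005 mSv (0.00005 rem"); for an earlier fluoroscopic knee replacement study, "average effective dose was 0.14 mSv (0.0014 rem) with a maximum dose of 0.27 mSv (0.0027 rem").
- **Other labels.** The earlier study's risk is called Negligible. A two-minute exam is said to range from Negligible to Low.
- **The risk scale.** Attachment 1, Table 4 relates effective dose in mSv to a risk and a verbal label. Its 1.0–10 mSv row (10⁻⁴, Very low) has the example "CT of the brain, chest, or abdomen". Its 10–100 mSv row (10⁻³, Low) has the example "Multiphase CT".

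**The concern.** The cap is given in rem and the risk table is in mSv, so the label depends on a unit conversion. Every mSv-to-rem conversion printed in the paragraph uses 0.01 rem per mSv, whereas the correct factor is 0.1. That alone calls for a check of the label.

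The paragraph is also inconsistent without any conversion. It gives Low as the upper end for a two-minute exam and then gives the lower label, Very Low, to a ceiling many times larger.

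At stake is the accuracy of the maximum dose and risk class put forward for up to 90 participants (45 per implant), for whom the Benefits section intends no direct benefit. The kinematic comparison itself is not affected.

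**Working it through.** **Conversion factor.** By definition 1 rem = 10 mSv, so 1 mSv = 0.1 rem = 100 mrem. The attachments agree:

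| Examination | Attachment 2 (mSv) | Attachment 4 (mrem) | mSv per rem |
|---|---|---|---|
| Chest PA | 0.02 | 2 | 0.02 / 0.002 = 10 |
| CT head | 2 | 200 | 2 / 0.2 = 10 |
| CT chest | 7 | 800 | 7 / 0.8 = 8.75 |
| Barium enema | 8 | 700 | 8 / 0.7 = 11.4 |

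These are averages from different sources, so they support the order of magnitude; the exact factor is the unit definition.

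**The plan's input.** The angiography rate reproduces: Attachment 1, Table 2 gives 5.0 mSv over 6 minutes, and 5.0 / 6 = 0.83 mSv per min. The mSv figures are not in dispute.

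**The cap under each possible reading.**

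| Reading of the cap | mSv | Table 4 row | Label |
|---|---|---|---|
| 4 rem at 10 mSv per rem (correct) | 4 × 10 = 40 | 10–100 | Low, 10⁻³ |
| 4 rem at the paragraph's 0.01 rem per mSv | 4 / 0.01 = 400 | >100 | Moderate, >10⁻² |
| Cap meant as 4 mSv (0.4 rem) | 4 | 1.0–10 | Very low, 10⁻⁴ |

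The stated Very Low is not reproduced under either conversion. It fits only if the cap was meant as 4 mSv, which the documents do not show. The mislabel is therefore not a by-product of the faulty conversions, which would push it the other way.

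**The four conversions** (mSv × 0.1):

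| mSv | Printed rem | Correct rem | Correct / printed |
|---|---|---|---|
| 0.83 per min | 0.0083 | 0.083 | 10 |
| 0.005 | 0.00005 | 0.0005 | 10 |
| 0.14 | 0.0014 | 0.014 | 10 |
| 0.27 | 0.0027 | 0.027 | 10 |

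**The other two labels.**

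- Earlier study: 0.14 and 0.27 mSv both lie in the 0.1–1.0 mSv row, *Minimal or extremely low* (10⁻⁵). Negligible is below 0.1 mSv. The printed label is one band too low.
- Two-minute exam: 2 × 0.83 = 1.66 mSv, which is Very low. The printed upper end, Low, is one band too high.

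**Distance between the cap and expected doses.**

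- Against the earlier study's maximum: 40 / 0.27 = 148. From the printed rem values it would look like 4 / 0.0027 = 1,481, so the apparent margin is inflated tenfold.
- Against the two-minute angiography estimate: 40 / 1.66 = 24.
- A cap at 10 mSv would be 10 / 0.27 = 37 and 10 / 1.66 = 6.0 times those doses.

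**The case against.** The strongest reply is that nothing happens differently to any subject. Exposure is controlled by beam time: the Data Collection section sets a two-minute limit and ALARA, on-time is recorded for each subject, and the Protocol itself thinks it unlikely that anyone will approach 4 rem. Even 40 mSv is below the roughly 100 mSv under which the position statement in Attachment 3 finds observed effects not statistically different from zero. All of this stands, and it limits the severity.

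A second reply is that the cap is not really ambiguous. The section gives it five times, always as 4 rem, and the label appears once, so the label is the likelier slip. That is reasonable, but repetition does not show that 4 rem was the intended number, and Very low would fit a cap of 4 mSv. The author has to say which was meant.

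Third, the two smaller mislabels carry little weight. The two-minute label overstates risk, and its range contains the correct band. The Negligible row lists extremity radiography as an example, which may explain the wording for the earlier study. Both are fair points; by dose, however, both labels are still off by one row.

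None of this makes the statement about the cap correct.

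**Conclusion.** The concern holds and should be fixed. The stated ceiling of 4 rem is 40 mSv, four times the upper edge of the band whose label it carries. The Protocol's own table gives 10⁻³ where the text claims the 10⁻⁴ category. The four rem conversions are each low by a factor of ten, and two further labels are off by one band, in opposite directions.

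This rests on the definition of the rem and on Table 4 being the scale behind the labels; it is the only table in the documents that uses them. The error lies in the stated ceiling and its description, not in the dose subjects are likely to receive. Whether participants were shown these figures cannot be checked from the documents available.

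**What to change.** 1. **Resolve the cap.** Either keep 4 rem and label it Low (10–100 mSv, 10⁻³), or, if Very Low was intended, have radiation safety lower the cap to less than 1 rem (10 mSv). *Less than* keeps it off the boundary between the two rows. State the cap in both mSv and rem.
2. **Correct the conversions** to 0.083 rem per min, 0.0005 rem, 0.014 rem and 0.027 rem.
3. **Correct the other labels.** The earlier study becomes *Minimal or extremely low*; the two-minute exam becomes Negligible to Very low.
4. **Carry the corrected figures** into any IRB or participant text that repeats them.

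The cost is a text amendment and IRB notification. Keeping 4 rem means accepting a less favourable stated risk class. Lowering the cap requires radiation safety to confirm the new limit; with every two-minute estimate in the Protocol below 2 mSv, there is ample room. Correcting the text requires no change to the imaging procedure.
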